5 STUDY SUMMARY

Table 3. Study Summary

| Table 3. Study Summary | |
|--------------------------|--|
| Study Title | A clinical investigation of an autonomous phone conversational agent for cataract surgery follow-up |
| Short title | Autonomous telephone follow-up after cataract surgery |
| Study Design | The study will be a multi-centre, mixed-methods clinical investigation to develop evidence regarding the feasibility, acceptability and potential effectiveness of DORA . |
| Study Participants | The study will include adults (aged 18 years or older) who are on the waiting list for either their first or second eye cataract surgery at Oxford or Imperial. To be eligible, the patients must have no history of significant ocular comorbidities and have a routine surgery with no intraoperative complications. |
| Planned Size of Sample | The planned sample size is 591 patients, split mostly equally between Oxford and Imperial clinical sites (see Table 1 for details on how this estimate was produced). |
| Follow up duration | Imperial: patients will receive the standard face-to-face appointment within a few days of having the autonomous call (dependent on current Covid-19 restrictions). |
| | Oxford: there will be no face-to-face follow-up for patients at the Oxford site as this is the standard of care. |
| | At both sites, an additional 3-month follow-up period where unplanned eye-related clinical visits will be recorded and assessed. |
| Planned Study Period | The total duration of the study will take up to 3 years, including the recruitment of patients, intervention refinement period, main intervention period, and analysis of results. |
| Research Question/Aim(s) | The aim of the study is to assess the evidence for the safety of using DORA to deliver autonomous cataract surgery follow-up assessments. This ability will be evaluated in comparison to an expert human clinician to assess the research question: Can DORA identify which patients need clinical follow up after a cataract operation? |

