7.4 Research Question

DORA was developed to provide an alternative for conducting post-cataract surgery follow up assessments to save nurses' and other clinicians' time. The key outcome of this study is evaluating **DORA's** ability to accurately identify which patients have postoperative complications which would justify specialist care, and assessing **DORA's** accuracy compared to an expert clinician. To assess this critical capability, the research question that this study will investigate is: Can **DORA** identify which patients need clinical follow up after a cataract operation?

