8.2.3 Intervention(s)

DORA uses a variety of AI technologies to deliver the patient follow-up call, including: speech transcription, natural language understanding, a machine-learning conversation model to enable contextual conversations, and speech generation. Together, these technologies cover the input, processing and analysis, and output needed to maintain a natural conversation. **DORA** is configured to deliver calls through a telephone connection as a real-time, stand-alone system: the operator inputs individual patient details to initiate the call and completes a summary in the electronic health record (EHR) afterwards. The call that patients will receive from **DORA** will include several conversational elements:

- Greeting and introduction
- Identification of patient
- Cataract follow-up questions
- Patient's queries
- (Decision)
- Questions about acceptability
- Closure of call

The entire conversation will be supervised by a clinician. This clinician will be able to interrupt the call at any point if the system fails, the patient struggles to interact with it, or **DORA** does not collect sufficient information from the patient. The call will proceed in the following stages (visualised in Figure 5):

- 1. Stage 1. Call initiation: the supervising clinician will confirm the suitability of the patient, input their details, and initiate the call.
- 2. Stage 2. Symptom assessment: Once the call has begun, **DORA** will verify the identity of the patient and proceed through the cataract follow-up questions. As the patient answers the questions, both **DORA** and the supervising clinician will record their independent assessment about the clinical significance of the symptoms elicited.
- 3. Stage 3. Management plan decision: Once all of the follow-up questions have been asked, **DORA** and the supervising clinician will independently make and record their decisions about the management plan for the patient. **DORA** will then inform the patient of the clinician's decision about their management plan (i.e. whether specialist review is required or not).
 - Stage 3a: Optionally, if required, the supervising clinician can ask additional clarifying questions.

Figure 5. Flow Diagram of DORA's call with patient

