8.2.5 Outcomes

8.2.5.1 Primary Outcomes

Agreement

The primary outcome of the study is to establish preliminary safety evidence by evaluating the level of agreement between **DORA** and the expert human clinician on symptom and overall management plan decisions.

To evaluate agreement, **DORA's** ability to classify five key symptoms from the conversation will be compared with a supervising clinician's classification of the same five symptoms: redness, pain, reduced vision, flashing lights, and floaters (see Table 5). For this study, the supervising clinician's decision - made based on the information from the call with **DORA's** decision masked - is considered the gold-standard for evaluation. Both **DORA** and the supervising clinician (masked to each other) will independently indicate for each symptom, whether the symptom is:

- 1. Absent (e.g. no pain)
- 2. Present but not clinically significant (e.g. mild gritty sensation)
- 3. Present and clinically significant (e.g. deep and persistent pain)
- 4. Insufficient information for classification

The agreement between **DORA** and the clinician on the patient's management plan will be evaluated in the same way as the symptoms. **DORA** and the clinician will independently select one of the following options for the patient's management plan:

- 1. Passes check (patient continues to next step of their care as planned, e.g., Discharge from hospital care, add to waiting list for second eye surgery, or continue routine follow-up in clinic for another ophthalmic condition)
- 2. Needs clinical assessment relating to the cataract surgery

Ability to gather sufficient information

To evaluate **DORA's** ability to gather enough information for a clinician to decide a patient's management plan and the necessity for the clinician to ask clarifying questions will be assessed. If clarifying points are necessary for the clinician to make a decision, the clinician will ask the necessary questions, and then document updated assessments for symptoms and overall management (see Figure 5). Either 12 or 18 data points will be collected from each call depending on if clarifying questions are asked.

• Every Conversation

- o 5 symptom decisions from DORA + 1 clinical decision from DORA
- o 5 symptom decisions from Clinician + 1 management plan from Clinician
- If clarifying questions asked
 - Post-clarification 5 symptom decisions from Clinician + 1 management plan from Clinician

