8.2.5.2 Secondary Outcomes

There will be several secondary outcome measures to assess the clinical safety, feasibility, usability, and acceptability of the system (see Table 6).

Clinical safety

To examine safety, two outcomes will be captured. Firstly, patients at both sites will have a retrospective case review of both general and ophthalmic electronic health records at 90 days after their initial operation. Complications will be identified from patient's medical records related to any unplanned eye-related clinical episode.

Secondly, all cataract surgery patients at Imperial were historically followed up face-to-face between 3-4 weeks post-surgery in a dedicated post-op clinic. Any complications requiring a change in patient management at slit lamp review or from attending eye casualty services (as the Oxford site does not normally perform face-to-face follow-ups) will be compared with the decisions made by **DORA** and the clinician. If Imperial changes their method of follow-up due to the COVID-19, assessment for complications will be done by checking hospital medical records as is done at the Oxford site.

Feasibility

Feasibility will be assessed by examining the proportion of autonomous calls that were completed without needing any intervention from the supervising clinician. All interruptions or clarifying questions of the supervised call will be logged; the supervising clinician will be asked to log the reason for asking clarifying questions. If clarifying questions were asked because the clinician felt that there was insufficient information for either individual symptoms or to make a management plan, the clinician's management plan before and after clarifying questions will be captured to see if clarifying questions changed the management plan.

Usability

Usability will be assessed using questions presented to patients following calls delivered by online and paper surveys distributed to participants. These questions will be drawn from the System

Usability Scale (SUS) and Telehealth Usability Questionnaire (TUQ; see 13.4 Appendix 4 for a sample survey) [14,15].

Acceptability, satisfaction, and appropriateness

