8.5 Data Analysis

8.5.1 Statistical Methods for Primary Outcome

The primary analysis will be the calculation of a kappa statistic of inter-observer (**DORA** & clinician) reliability of the decision made. Additionally, the outcome of the assessment will be compared with the 'real' complication rate determined by hospital medical records. This will be established by identification of any hospital presentation within 90-days after the last call. Given the specialist nature of ophthalmology services it can be assumed that patients will present through the eye casualty or clinic services offered by each site. Patients who present to the hospital eye service will be analysed on a case-by-case basis to ensure that complications that were missed by **DORA's** original assessment and complications that developed later can be differentiated. This analysis will provide baseline sensitivity and specificity data for use in preparing subsequent evaluations of efficacy.

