A Clinical Investigation of an Autonomous Phone Conversational Agent for Cataract Surgery Follow-up

NCT05213390

30 August 2022

Statistical analysis plan

Using the variables:

- doraoutcomeupdate (0 = pass, no review, 1 = fail, needs review)
- supervisoroutcomeupdate (0 = pass, no review, 1 = fail, needs review)

Primary outcome: Agreement between Dora and clinician for overall outcome decision and each symptom (x5)

- Inter-rater reliability (kappa)
- Accuracy (%)
- Data regarding true/false negatives/positives

	Clinician: follow-up (1)	Clinician: no follow-up (0)
Dora: follow-up (1)	ТР	FP
Dora: no follow-up (0)	FN	TN

• Sensitivity, specificity, AUC

Secondary outcomes

Clinical safety: Comparison with real complication rate

*Note: please do this analysis three times, once for each of the three complication measures
Data regarding true/false negatives/positives (Tables 2-3)

	Complications: 3 month audit	No complications: 3 month audit
Dora: follow-up	ТР	FP
Dora: no follow-up	FN	TN

- Sensitivity, specificity, AUC
- Variables
 - Dora follow up: "doraoutcomeupdate"
 - Complications:
 - "hospital-review-within-3-months"
 - 0 = no hospital review, 1 = hospital review
 - "unexpected-change-management"
 - 0 = no unexpected change management, 1 = unexpected change management

EUR ING [name] MA MSc MBA MPA PhD CEng FBCS Associate Professor of eHealth

"unplanned-hospital-rev"

• 0 = no hospital review, 1 = hospital review

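### The protocol promises that management-change complications will be compared with both DORA's and the clinician's decisions; the SAP's safety analysis uses DORA's decision only

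*SAP*

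**What the plan says.** Protocol section 8.2.5.2 (Clinical safety) sets two safety outcomes. The second covers "Any complications requiring a change in patient management at slit lamp review or from attending eye casualty services", and these are to be "compared with the decisions made by DORA and the clinician". If Imperial stops face-to-face follow-up because of COVID-19, complications there will be taken from hospital records, as at Oxford.

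The SAP defines two decision variables at the top, `doraoutcomeupdate` and `supervisoroutcomeupdate`. It uses both for the primary agreement analysis. Under clinical safety the 2x2 has DORA in the rows and complications in the columns, and the variable list reads "Dora follow up: 'doraoutcomeupdate" with no clinician entry. The analysis is to be run three times, once per complication measure (`hospital-review-within-3-months`, `unexpected-change-management`, `unplanned-hospital-rev`). It is not repeated for the second rater.

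The wider aim is comparative. The Study Summary says "This ability will be evaluated in comparison to an expert human clinician", and section 7.4 speaks of DORA's "accuracy compared to an expert clinician".

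**The concern.** A complication that DORA passed can have two explanations. If the clinician listening to the same call passed the patient too, the miss points to a limit of the telephone call. If the clinician flagged the patient, it points to DORA. These mean different things for safety, and the planned output gives only DORA's total of false negatives.

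The clinician's masked decision is also the gold standard for the primary outcome (section 8.2.5.1). The comparison promised in section 8.2.5.2 is the place where that standard would be checked against what happened to patients, and the SAP leaves it out.

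**Working it through.** **Text comparison.** The documents give no figure on this point, so the check is of wording first.

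- Protocol 8.2.5.2: management-change complications against DORA and the clinician.
- SAP, clinical safety: complications against `doraoutcomeupdate` only.
- SAP, primary outcome: DORA against the clinician, with no complication variable.
- Protocol 8.2.4, Table 6 and 8.5.1 describe the safety comparison in terms of DORA or the DORA call. None withdraws the sentence in 8.2.5.2.
- The case-by-case review in 8.5.1 is there so that complications missed by DORA and "complications that developed later can be differentiated". It does not separate misses that the clinician shared.

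**Can the missing comparison be recovered from the planned tables?** Let E be the patients with a complication, TP and FN DORA's results among them, b all patients flagged by DORA only, and c all flagged by the clinician only. Then

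clinician TP = TP − (DORA-only flags among E) + (clinician-only flags among E).

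The planned tables give b and c overall but not among E. The clinician's sensitivity is therefore fixed only to between (TP − min(b, TP))/E and (TP + min(c, FN))/E, provided the remaining discordant patients fit among those without a complication.

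Illustration on assumed counts, not from the documents: 286 patients, 56 flagged by both, 14 by DORA only, 14 by the clinician only, 202 by neither.

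- Agreement = (56 + 202)/286 = 0.902.
- Chance agreement = (70² + 216²)/286² = 0.630.
- Kappa = (0.902 − 0.630)/(1 − 0.630) = 0.74.
- With E = 80 and TP = FN = 40, clinician sensitivity lies between (40 − 14)/80 = 32.5% and (40 + 14)/80 = 67.5%.

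So good agreement does not settle the question. The width depends on the assumed counts.

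**Expected events at Imperial.** The site total in Table 7 reproduces:

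- One-stop: 10 × 2 × 0.4864 × 0.70 × 26 × 0.85 = 150.5.
- Pre-assessment: 8 × 2 × 0.5472 × 0.70 × 26 × 0.85 = 135.4.
- Sum: 286.

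Appendix 6 reports 7 of 25 patients with a complication requiring a management change. It prints 21% beside this, but 7/25 = 28%; 21% matches 7/33, and 33 is all booked patients. I use 7/25.

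- 286 × 7/25 = 80 events.
- The exact 95% interval for 7/25 is 12.1% to 49.4%; the lower limit gives 286 × 0.121 = 35 events.

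**Precision of the paired difference** (DORA minus clinician sensitivity, Tango score interval, discordance assumed equal each way):

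| Events | Discordant | 95% half-width |
|---|---|---|
| 80 | 8 (4 + 4) | ±8.0 points |
| 80 | 16 (8 + 8) | ±10.4 points |
| 35 | 4 (2 + 2) | ±14.1 points |

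**Why the difference should not be taken for hospital reviews.** Under section 8.2.3 the patient is told the clinician's decision. A clinician-only flag can lead to a review; a DORA-only flag cannot. Take Oxford's 305 patients, with assumed flags: 30 by both, 10 by DORA only, 10 by the clinician only, 255 by neither. Suppose every clinician flag leads to a review and 1/30 of the rest attend anyway (Appendix 7: 1 of 30 operated patients attended the emergency department).

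- Reviews = 40 + 265/30 = 48.8.
- Clinician sensitivity = 40/48.8 = 82%.
- DORA sensitivity = (30 + 10/30)/48.8 = 62%.

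That is a 20-point gap between raters with identical flag rates. It is the extreme case, and partial uptake would shrink it.

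**The case against.** The strongest reply is that the expert comparison is already delivered. The primary analysis gives kappa, accuracy, sensitivity and specificity of DORA against the clinician, and neither the Study Summary nor section 7.4 asks for the clinician's own sensitivity to complications. Objective 2 and section 8.5.1 concern DORA. The promise rests on one sentence that names no statistic, and a descriptive listing might satisfy it. This stands in part: the sentence does not demand a paired difference or an interval, and those are my proposal. But agreement with the clinician does not show whether either rater detects complications, and the SAP contains no listing either.

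The SAP cites Tables 2-3 while one safety table is visible, so a table may have been lost in extraction. The legible variable list still names only DORA's decision.

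A reader might go further and infer that the information is lost, or that all three complication measures should carry the two-rater comparison. The documents support neither. Both decisions are recorded for each patient, so the cross-tabulation can be run without new data. Section 8.2.5.2 makes the promise only for management-change complications, and for the two hospital-review measures the contrast would be biased towards the clinician. Nor does the range of 32.5% to 67.5% measure the defect; it only illustrates that the planned tables leave the answer open.

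**Conclusion.** The mismatch is real and worth correcting before the analysis is run. A comparison that the protocol commits to on a safety outcome is missing from the SAP, and it cannot be rebuilt from the tables that are planned. The sample size and the primary analysis are unaffected.

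The gain is moderate. The precision figures assume that all 286 Imperial patients have the visit (24 of 25 attended in the audit), that the audit rate carries over although the audit covered one-stop patients only, and that discordance is balanced. If Imperial moves to record review, only the counts are useful.

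Even at Imperial the contrast needs care. The operator "completes a summary in the electronic health record (EHR) afterwards", the patient knows the clinician's decision, and nothing in the documents masks the face-to-face examiner to the call result. Both raters also judge one shared call, so a reader should not take this as a test of DORA against independent human follow-up.

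**What to change.** For `unexpected-change-management`, add to the SAP:

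1. The same 2x2 with sensitivity and specificity for the clinician's decision.
2. Among patients with a complication, the number flagged by both, by DORA only, by the clinician only and by neither.
3. For Imperial patients who had the face-to-face visit, the paired DORA-minus-clinician sensitivity difference with a score-type 95% interval, as estimation with no test. Elsewhere, report the four counts only.
4. A statement that the paired difference is not calculated for the two hospital-review measures, because a clinician flag can itself create the review.
5. The source (site, visit or records) of `unexpected-change-management`, which the SAP does not give.

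Use the clinician's masked decision from before any clarifying questions, so that both raters are judged on the same information. After such questions the clinician is to "document updated assessments for symptoms and overall management", so confirm which decision `supervisoroutcomeupdate` holds. State the limits given above with the results. If the clinician comparison is left out on purpose, say so and give the reason.

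Cost: a few lines of SAP and code. If the variable holds the post-clarification decision, one data pull of the earlier record is also needed. No new patients or visits are required.

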6 STUDY FLOW CHART

Patients receiving usual care for cataract surgery typically progress through four stages. Participants in this study will undergo two additional stages that are specific to the study (stages 4 and 6). There are six stages that participants of the study will potentially go through. These stages, and their approximate timeline, are visualised in the flow diagram below (Figure 1).

- 1. Stage 1. The patient is referred by a clinician for cataract surgery.
- 2. Stage 2. The patient's suitability for surgery is determined at a pre-assessment appointment or a one-stop cataract clinic. Patients who meet the eligibility criteria for the study at this stage will be provided with a participant information sheet (see 13.1 Appendix 1) and, if they are willing to participate, informed consent will be collected (see 13.2 Appendix 2).
- 3. Stage 3. The patient undergoes their scheduled cataract surgery. If the surgery was uncomplicated, a patient may also consent to participate in the study in the recovery lounge.
- 4. Stage 4. If the patient is consented to participate in the study, they will receive a follow-up call from DORA (supervised by a clinician). The call script used by DORA will be reviewed by supervising PIs in advance in order to reduce incidence of non-compliance through misunderstanding.
- 5. Stage 5. If the patient had the surgery at Imperial, regardless of whether or not they are participating in the study, they will have a scheduled follow-up with a clinician.
- 6. Stage 6. If the patient consented to participate in the study, they may be randomly selected to participate in a semi-structured interview, to provide more in-depth feedback about their experience using **DORA**.

Figure 1. Participant flow diagram

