8.2.4 Comparator(s)

Imperial sees all of their post-operative cataract patients at a face-to-face out-patient appointment with an ophthalmologist or specialist nurse. This is conducted between three to four weeks following the procedure. Therefore, patients at Imperial will receive their call from **DORA** within 3 days before their scheduled appointment (day 25-27 post-surgery). This will enable the results of the **DORA** call to be compared with the face-to-face appointment at Imperial to assess whether any complications were correctly identified and if the management plan remains the same.

For patients at both clinical sites, health records will be examined 90 days after the call to determine if the patient presented to an eye clinic with any complications from surgery. This comparison of the follow-up with actual complication rate will enable an assessment of **DORA's** safety (see Table 6).

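### One of the SAP's three complication references does not exclude scheduled visits, so its table can understate DORA's sensitivity; separately, the 90-day window has two different starts

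*SAP*

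**What the plan says.** **SAP, Secondary outcomes, Clinical safety.** The same 2x2 analysis of DORA's decision (sensitivity, specificity, AUC) is run on three complication measures: "hospital-review-within-3-months", "unexpected-change-management" and "unplanned-hospital-rev". The first and third carry identical value labels (0 = no review, 1 = review). None is defined further, none is named as the main one, and pooling or splitting by site is not mentioned.

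**Protocol, what the record review is for.** The Study Summary (section 5) says that over three months "unplanned eye-related clinical visits will be recorded and assessed". Section 8.2.5.2 likewise refers to unplanned episodes. Section 8.5.1 is broader, taking any presentation at the hospital, but adds a case-by-case review to separate complications that DORA missed from those that developed later.

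**Protocol, scheduled visits.** Section 8.2.4 states that "Imperial sees all of their post-operative cataract patients at a face-to-face out-patient appointment", with the DORA call on day 25-27, within three days before that visit. Stage 5 of the flow chart (section 6) says of Imperial patients that "they will have a scheduled follow-up with a clinician". The Study Summary makes the Imperial visit "dependent on current Covid-19 restrictions". For the other site it says that "there will be no face-to-face follow-up for patients at the Oxford site".

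**Protocol, window.** The 90 days run from the operation in 8.2.5.2 and Table 6, from the call in 8.2.4, and from the last call in 8.5.1.

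**The concern.** Objective 2 is to establish baseline sensitivity and specificity for detecting postoperative complications. A reference that counts scheduled attendance as a complication cannot do that. Where DORA correctly passes a well Imperial patient who then keeps the routine appointment, the SAP table scores a false negative. Because only Imperial schedules such visits, the reference would also partly be a marker of site.

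The window matters for a different reason: its start decides how many days after the call are searched for missed complications.

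**Working it through.** **1. The plan's own denominators.** Table 7, per stream: patients per clinic x 2 screening days x compound eligibility x 0.70 consent x 26 weeks x 0.85 retained.

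- Imperial one-stop: 10 x 2 x 0.4864 x 0.70 x 26 x 0.85 = 150.5
- Imperial pre-assessment: 8 x 2 x 0.5472 x 0.70 x 26 x 0.85 = 135.4
- Oxford pre-assessment: 12 x 2 x 0.6156 x 0.70 x 26 x 0.85 = 228.6
- Oxford telephone: 4 x 2 x 0.6156 x 0.70 x 26 x 0.85 = 76.2

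The site totals are 285.9 and 304.7, which agree with the printed 286, 305 and 591.

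**2. Audit rates.** Imperial (Appendix 6): 7/25 = 28% had a complication that changed management at the post-operative visit. The percentage printed there is 21%; I use the counts. Oxford (Appendix 7): 1 of 30 operated patients attended, 3.3%.

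**3. Formulas.** Let a and b be the shares of Imperial and Oxford patients with any hospital review, and assume that every patient with a complication is reviewed.

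- Real complications = 286 x 7/25 + 305/30 = 80.1 + 10.2 = 90.2
- Reference-positives = 286a + 305b
- Sensitivity of an error-free DORA = 90.2 / positives
- Share of positives that are Imperial visits without a complication = (286a - 80.1) / positives
- A rule that flags every Imperial patient and no Oxford patient has sensitivity 286a / positives, specificity 305(1-b) / [286(1-a) + 305(1-b)], and AUC equal to the mean of the two

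| Case | Positives | Error-free sensitivity | Routine share | AUC of site alone |
|---|---|---|---|---|
| a = 1, b = 1/30 | 296.2 | 0.305 | 0.695 | 0.983 |
| a = 24/25 (audit attendance), b = 1/30 | 284.7 | 0.317 | 0.683 | 0.963 |
| a = 1, b = 0.2 (assumed) | 347.0 | 0.260 | 0.593 | 0.912 |
| a = 0.5 (assumed), b = 1/30 | 153.2 | 0.589 | 0.411 | 0.804 |

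**4. Uncertainty in the audit rates.** The exact 95% limits are 12.1-49.4% for 7/25 and 0.1-17.2% for 1/30. At a = 1, with both rates at the lower or both at the upper limit, error-free sensitivity runs from 0.122 to 0.572. With the printed 21% it is 70.2/296.2 = 0.237.

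**5. When routine visits are the majority.** Setting the routine share to one half gives a = (80.1 + 0.5 x 305b)/143, which is 0.596 at b = 1/30 and 0.773 at b = 0.2.

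**6. Window.** For a call on day 25-27, a window from the operation leaves 90 - 25 = 65 to 90 - 27 = 63 days after the call, against 90 from the call. A call-based window ends on day 115-117. Imperial's scheduled visit falls inside either window. Oxford's call day is not given, so the difference there cannot be computed.

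**The case against.** **The coding is inferred.** The SAP gives a name and two value labels. The table heading refers to the three-month audit, which the protocol ties to unplanned episodes, so an unwritten restriction is possible. The two similar variables might also differ only in their time window. This stands: a reader might infer that planned visits are definitely included, and the SAP does not say so. It is still true that the text does not exclude them, and that following it literally gives the wrong answer.

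**Imperial's visit may not continue.** Section 8.2.5.2 describes it as historical practice and provides a records-based fallback. This also stands. A reader might infer that most positives will be routine visits; by step 5 that needs about 60% of Imperial patients to be reviewed, or 77% if a fifth of Oxford patients are. The error itself does not need a majority, as the half-reviewed case shows.

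**Safeguards exist.** Table 6 already sets separate comparisons for Imperial and Oxford, 8.5.1 requires case review, and two other references are reported alongside. True, and this limits the damage. The SAP, however, does not say that the references are coded after that review.

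**The illustration is fragile.** It projects 25 and 30 audited patients onto 591. The Imperial audit covered one-stop clinics only. Oxford follow-up averaged at most about 82 days if the report date was the data cut-off (112 days from 1 October 2020 to 21 January 2021, less a mean of 30 to surgery). The direction of the error follows from the coding; its size is uncertain.

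**Two further readings go too far.** One could apply the audit rates to "unexpected-change-management" and infer that Imperial supplies 80.1/90.2 = 89% of its positives. That equates audit counts with a variable the SAP does not define. One could also count three window starts, but the call and the last call coincide for anyone called once, so there are in substance two.

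**The window effect may be small.** Patients with an unplanned review before the call are withdrawn (8.3.1.3), and the Oxford audit contacts at 6 and 10 weeks fall inside either window. Fair: lost days are shown here, not lost events.

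**Conclusion.** The point holds in conditional form and should be fixed. Coded literally, with Imperial's scheduled review running, one of three safety tables would understate DORA's sensitivity and its pooled results would largely reflect site. An error-free DORA would show about 30% with all Imperial patients reviewed, which is near the extreme, and 59% with half reviewed. These figures rest on Table 7, small audits, and the assumption that every complication leads to a review.

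The primary kappa analysis is unaffected. The other two references lack this particular fault, although they too are undefined. The window conflict is a plain inconsistency in the protocol and needs no assumption. Confidence is moderate, because the intended definition of the variable is not in the documents.

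**What to change.** 1. Exclude scheduled visits from "hospital-review-within-3-months" when it serves as a complication reference, or report it only as a utilisation count. If it already excludes them, state this in the SAP and say how it differs from "unplanned-hospital-rev".
2. Define the complication references and code them after the case-by-case review that 8.5.1 already requires, listing later-onset complications separately from missed ones.
3. Report each safety 2x2 table by site as well as pooled, in line with Table 6 and with the caution in 8.6 about comparing the sites.
4. Reconcile the window start across 8.2.4, 8.2.5.2, Table 6, 8.5.1 and the SAP.

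Which reference is the main one, and which start is used, is for the sponsor to choose.

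The cost is SAP definitions, some recoding, extra tables, and wording edits in the protocol places that do not match the chosen start. No additional patients are needed. Record review would have to be extended only under a call-based window, to about day 115-117 after surgery at Imperial.
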